10	12/27/2019	
Added Guild and Fairview sites and recruitment procedures for Study 2 (letters of support attached)	Yes

PROTOCOL TITLE: Increased thalamocortical connectivity in tDCS-potentiated generalization of cognitive training

VERSION DATE: January 26, 2023

		
• Added Release of Information for Guild patients to protocol and consent• Added assessment audio/video recording to protocol and consent• Added language describing payments for additional visits• Added psychosis history questionnaire• Removed Department of Psychology database from section 16• Added CMRR servers to section 16• Removed magnetic and optical media from sections 6 and 16• Modified the estimated IQ inclusion criteria range and uploaded updated IQ screen form	
9	9/30/2019	
• Added compensation to CEDT	Yes
8	9/5/2019	
• Changed exclusion criteria regarding psychiatric diagnoses to exclude only Serious and Persistent Mental Illness• Clarified exclusion criteria regarding conditions with neurological sequelae to exclude concussion with hospital admission	No
7	7/25/2019	
• Clarified that Cohort 2 participants may be recruited and screened using the online portal• Explained visit timeline windows• Replaced the PANSS with the BPRS and BNSS• Clarified that UBACC will be used in both cohorts• Explained that blinding code will be maintained by study statistician• Changed randomization procedure description• Clarified that some sensitive data is stored on secure servers (in addition to locked cabinets)• Added consent language about costs of participation per updated guidelines	Yes
6	6/20/2019	
• Clarified MRI contraindications and procedure for determining MRI safety clearance for subjects	No
5	5/23/2019	
• Removed “6-panel” specification from drug screen language.	No

PROTOCOL TITLE: Increased thalamocortical connectivity in tDCS-potentiated generalization of cognitive training

VERSION DATE: January 26, 2023

PROTOCOL TITLE: Increased thalamocortical connectivity in tDCS-potentiated generalization of cognitive training

VERSION DATE: January 26, 2023

ABBREVIATIONS/DEFINITIONS

FC	functional connectivity
HC	healthy controls
MD	modeled dosage
tDCS	transcranial direct current stimulation
WM	working memory
SZ	schizophrenia or schizoaffective disorder
DNA	deoxyribonucleic acid
BDNF	brain-derived neurotrophic factor

PROTOCOL TITLE: Increased thalamocortical connectivity in tDCS-potentiated generalization of cognitive training

VERSION DATE: January 26, 2023

STUDY SUMMARY

Study Title	Increased thalamocortical connectivity in tDCS-potentiated generalization of cognitive training
Study Design	Randomized Controlled Trial, Triple Blind
Primary Objective	To understand how tDCS with cognitive training affect thalamocortical circuitry in individuals with and without psychosis and to examine variability in response within both groups.
Secondary Objective(s)	To associate genotypes and epigenetic changes with variations in treatment response and outcome.
Research Intervention(s)/Investigational Agents	Transcranial direct current stimulation and magnetic resonance imaging
IND/IDE # (if applicable)	N/A
IND/IDE Holder	N/A
Investigational Drug Services # (if applicable)	N/A
Study Population	Healthy controls and individuals with schizophrenia
Local Sample Size (number of participants recruited locally)	180

PROTOCOL TITLE: Increased thalamocortical connectivity in tDCS-potentiated generalization of cognitive

training

VERSION DATE: January 26, 2023

1.0 Objectives

1.1 Purpose:

The overarching goals of this proposal are to deploy neuroimaging and cognitive testing to understand how tDCS with cognitive training affect thalamocortical circuitry in individuals with and without psychosis and to examine variability in response within both groups.

1.2 Secondary objective:

To associate genotypes and epigenetic changes with variations in treatment response and outcome.

2.0 Background

2.1 Significance of Research Question/Purpose:

The premise of the proposed work is that tDCS concurrent with multi-session working memory (WM) focused cognitive training facilitates durable increases in thalamo-prefrontal cortical (hereafter thalamocortical) functional connectivity (FC), and that this in turn enhances generalization to novel tasks. Due to its putative effects on plasticity and brain circuitry, tDCS is emerging as an important tool that may eventually be part of the next generation of psychiatric and neurological interventions (Andre Russowsky Brunoni et al., 2012). However, given the simple and non-focal nature of this intervention, significant questions about the mechanisms of action relevant to cognition remain unanswered (Bikson, Name, & Rahman, 2013; Flavio Fröhlich & Schmidt, 2013). Given that a 2 mA current from tDCS induces a low electrical field that causes subthreshold membrane polarization and does not carry any biological information, how can it potentiate improved performance on complex cognitive tasks or reduce diverse symptoms (Andre R. Brunoni et al., 2014; Kekic, Boysen, Campbell, & Schmidt, 2016; Trumbo et al., 2016)? Most critically for the current application, can understanding the neuroanatomy of tDCS-induced functional changes aid in optimizing tDCS for clinical applications?

2.2 Preliminary Data:

We have demonstrated that WM focused training increases left middle frontal gyrus (MFG) activity. This was first reported in a sample of n=9 experiment subjects with schizophrenia (compared to n=9 in the active control condition (Haut, [name], & [name], 2010)), and was recently replicated in n=15 patients (compared to n=12 in the active control (Ramsay, [name], Marggraf, & [name], 2017)). We observed significantly greater increases in connectivity following WM training compared to the active control treatment in both right MFG ($\eta^2=.35$) and ACC ($\eta^2=.29$). These effects were driven by increased thalamocortical connectivity in the experimental group. Importantly, those who showed the greatest increases in thalamocortical connectivity also had the most general transfer on the MCCB in the experimental group ($r=.55$, $p=.043$, but not in controls).

As a proof-of-concept, we have also directly examined thalamo-prefrontal functional connectivity before and after tDCS intervention. To determine whether tDCS can directly affect thalamocortical connectivity, subjects were randomized to either active tDCS (n=6) or sham tDCS (n=5). Rest fMRI data was collected pre- and post-intervention. Intervention consisted of either cognitive training + active-tDCS or cognitive training + sham-tDCS twice a day (two 13 minute sessions per day, each 2mA / 25cm² = 0.08 current density; anode on left dorsolateral prefrontal cortex F3, cathode on right dorsolateral prefrontal cortex F4) for five consecutive days. Preliminary analyses examining FC between left thalamus and left dorsolateral prefrontal cortex showed that subjects assigned to active-tDCS (n=6) showed a within-group increase in FC ($t=2.05$, $p=0.096$) while subjects assigned to sham-tDCS (n=5) did not show a significant within-group FC change ($t=1.103$, $p=0.332$). Group x Time effects was eta-square $\eta^2=0.353$. These pilot data suggest tDCS can improve thalamocortical connectivity.

PROTOCOL TITLE: Increased thalamocortical connectivity in tDCS-potentiated generalization of cognitive training

VERSION DATE: January 26, 2023

2.3 Existing Literature:

Task-dependent Nature of tDCS-enhanced Neuronal Plasticity. A growing consensus suggests tDCS acts as a modulator of ongoing synaptic activity to facilitate task-relevant plasticity. For example, anodal tDCS enhanced the induction of long-term potentiation (LTP) between concurrently active neurons in slice, but had no effect on inactive neurons (Kronberg, Bridi, Abel, Bikson, & Parra, n.d.). In living mice, a combination of training with stimulation enhanced both cortical LTP and motor learning in contrast to stimulation alone (Fritsch et al., 2010). This underscores the need for ongoing cognitive activity to realize the potential of tDCS.

TDCS-enhanced Cognitive Training. A major limitation of direct tDCS-enhancement of working memory (WM) appears to be that, upon meta-analysis, it leads to increased speed without increased accuracy on WM tasks (André Russowsky Brunoni & Vanderhasselt, 2014). Given this limitation, protocols interested in broader cognitive effects in healthy populations are increasingly using concurrent tDCS stimulation with training, such as WM training (e.g. 10 sessions, 2 mA left DLPFC, (Martin et al., 2013); 10 sessions, 1.5 mA left DLPFC, (Richmond, Wolk, Chein, & Olson, 2014); 7 sessions, 2 mA right and left DLPFC, (Au et al., 2016)). While tDCS-enhanced cognitive training, has only begun to be explored, there is evidence for greater training effects when training begins (Ramsay, [name], & [name], 2016) and better generalization with right DLPFC stimulation (Au et al., 2016). However, as with single session tDCS-enhanced training (Trumbo et al., 2016), broad generalization of training with this number of sessions has shown limited results (none (Richmond et al., 2014) or a few tasks (Au et al., 2016; Martin et al., 2013; Martin, Liu, Alonzo, Green, & Loo, 2014)).

Thalamus and the Role of Thalamocortical Connectivity in Cognitive Generalization. We reject the hypothesis that tDCS-enhanced WM focused training works simply by enhancing local prefrontal cortical activity. Extensive animal research suggests that thalamocortical connectivity plays a key role in (i) modulating the attentional resources of the frontoparietal executive network (Zikopoulos & Barbas, 2007a), (ii) facilitating cognitive processes through connectivity throughout prefrontal cortex (Xiao, Zikopoulos, & Barbas, 2009), and that (iii) serving as a marker to investigate specific aspects of psychiatric illness (Zikopoulos & Barbas, 2007b). Our human studies suggest that WM focused training enhances DLPFC activity without evidence of generalization (Haut et al., 2010; Ramsay et al., 2016), which is consistent with local Hebbian mechanisms that support specialization (Marssolek, 2008). In contrast, the relationship between the thalamus and prefrontal-parietal circuitry has long been implicated in the general cognitive ability (or intelligence) literature (Fangmeier, Knauff, Ruff, & Sloutsky, 2006; Haier, Siegel, Crinella, & Buchsbaum, 1993; Osherson et al., 1998). While a review of thalamic architecture and its reciprocal connections to prefrontal cortex is beyond our scope, it bears mentioning that thalamus is the central hub for communication between sensory, association and motor regions, with thalamic nuclei projecting to cortical and subcortical areas throughout the brain and in a diffuse manner, terminating in various layers of cortex (Jones, 2009). Impairments in this hub function are linked to WM failures (Bor et al., 2011). Below we present pilot data suggesting the extent to which thalamocortical connectivity is enhanced in WM training predicts the extent to which generalization is observed. Importantly, tDCS enhances thalamocortical connectivity: anodal stimulation over left DLPFC or motor cortex (M1) temporarily increased thalamocortical cortex connectivity to their respective regions (Polanía, Paulus, & Nitsche, 2012) (Keeser et al., 2011) (Sours, Alon, Roys, & Gullapalli, 2014).

Cognitive and Thalamocortical Connectivity Impairments in Patients with Schizophrenia (SZ). Cognitive deficits are a prominent feature of schizophrenia and represent a large unmet treatment need with consequences for functioning (Barch & Sheffield, 2014; Green, 1996; Sheffield et al., 2014). Cognitive training is an intervention designed to improve cognition through repetitive practice with the goal of improving cognitive performance such as attention, memory, and problem solving (Cassetta & Goghari, 2016). While cognitive training is effective for improving cognitive abilities for some patients (Bosia et al., 2016), the process is time

PROTOCOL TITLE: Increased thalamocortical connectivity in tDCS-potentiated generalization of cognitive training

VERSION DATE: January 26, 2023

and resource intensive (with as many as 48 1-hour sessions recommended) and many interventions show a lack of generalization (Dickinson et al., 2010). At the same time an increasingly compelling literature links thalamocortical FC impairments with schizophrenia, suggesting hyperconnectivity between thalamus and sensory regions (e.g. (Atluri, Steinbach, [name], Kumar, & [name], 2014)), and hypoconnectivity with prefrontal regions (e.g.(Anticevic et al., 2014)). The magnitude of hypoconnectivity even predicted conversion to psychosis among at-risk youth (Anticevic et al., 2015). Our findings, described below, that WM focused training improves thalamocortical connectivity in chronic patients with schizophrenia is therefore a hopeful advance in need of replication and extension (Ramsay et al., 2016).

Transcranial Direct Current Stimulation (tDCS) Studies in Schizophrenia. Various studies have reported promising effects of tDCS on medication-refractory clinical symptoms in schizophrenia (Brunelin et al., 2012; Andre R. Brunoni et al., 2014; F. Fröhlich et al., 2016; Goyal, Kataria, & Andrade, 2016; Shivakumar et al., 2013; Subramaniam et al., 2015), however the literature on tDCS's independent effect on cognitive deficits is quite mixed. Anodal stimulation showed small effects on attention (Smith et al., 2015), WM (Palm et al., 2016; Smith et al., 2015) but see also (Hoy, Arnold, Emonson, Daskalakis, & Fitzgerald, 2014) for a negative finding), memory (Smith et al., 2015) and general cognitive ability (Rassovsky et al., 2015; Smith et al., 2015). Marginal or negative effects were observed for processing speed (Palm et al., 2016; Smith et al., 2015). Cathodal stimulation showed comparably small results (Rassovsky et al., 2015). Our quantitative review of these findings failed to reject the null hypothesis in any domain of cognition for any modality of transcranial stimulation. Consistent with task-dependent nature of tDCS-enhanced neuronal plasticity, tDCS had its largest impact on SZ patients' cognitive impairments when repeatedly paired with concurrent WM cognitive training ([name], [name], & [name], 2016). This finding from our group is the clinical lead this study will replicate and examine.

Variance in Modeled Dosage. Physiological and behavioral responses to tDCS show high variability between participants. One possible source of variability in outcome is a variability in the induced electric field strength from participant to participant for identical electrode montages and applied intensities (Laakso, Tanaka, Koyama, De Santis, & Hirata, 2015; López-Alonso, Cheeran, Río-Rodríguez, & Fernández-Del-Olmo, 2014; Opitz et al., 2016; Wiethoff, Hamada, & Rothwell, 2014). Computational approaches have the potential to account for this variability using numerical methods to estimate the electric field distribution on an individual level. So far it has been untested whether numerical models can predict subject-specific variability in the response to tDCS. Recent intracranial field measurements (Huang et al., 2017; Opitz et al., 2016) and modelling studies (Laakso et al., 2015) have shown that applying a fixed intensity of 1mA can lead to large variations in the electric field strength in the brain across individuals. This variation in effective dose is a likely cause of the large interindividual variations in the physiological response to tDCS across participants (López-Alonso et al., 2014; Wiethoff et al., 2014). The possibility of computational models to account for this variability arising from interindividual anatomical variations (Opitz, Paulus, Will, Antunes, & Thielscher, 2015) has recently been recognized (Bestmann & Ward, 2017; Peterchev, 2017). Here we will directly test, whether individual realistic finite element method (FEM) models can account for observed variation in physiological and behavioral responses to tDCS.

The results from the proposed study on the effect of tDCS on thalamocortical connectivity in the context of WM focused training will provide critical information to inform future research work and clinical intervention studies.

Genetics and Treatment Response. Another source of treatment response variability could stem from differences between participants in baseline genetic profiles or epigenetic changes over the course of treatment.

PROTOCOL TITLE: Increased thalamocortical connectivity in tDCS-potentiated generalization of cognitive training

VERSION DATE: January 26, 2023

Schizophrenia and associated spectrum disorders have a strong genetic component, with recent studies estimating nearly 80% heritability (Hilker et al., 2018). Genetic polymorphisms, particularly in genes relating to the dopaminergic and serotonergic systems, have been associated both with the development of the disorder (Harrison, 2015) as well as with varied response to pharmacologic treatments (Arranz & De Leon, 2007; McClay et al., 2011). Genetic polymorphisms, especially in genes important for neuroplasticity, may also mediate neuroplastic changes underlying the effects of tDCS (Chhabra et al., 2016), as has been demonstrated with gene BDNF (Antal et al., 2010; Fritsch et al., 2010). In light of these genetic influences on key tenants of our study--i.e. treatment response in schizophrenia and physiological effects of tDCS--we will collect genetic samples from participants to determine whether genetic or epigenetic variations may affect response to the cognitive training and tDCS intervention. This information may help inform the development of more individually-tailored treatment protocols in the future. As this is a secondary aim, participants will be given the choice in the consent form to opt in or out of the genetic sampling procedure.

Substance use as a moderator and outcome variable of tDCS. Individuals with schizophrenia and related disorders tend to exhibit high levels of substance use, particularly nicotine, alcohol, and cannabis (Margolese et al., 2004). Use of these substances has been demonstrated to be both an outcome and moderator variable in tDCS interventions. Smoking, in particular has been shown to attenuate the effects of a tDCS intervention on auditory hallucinations in schizophrenia (Brunelin et al., 2015), but also to restore impaired tDCS-related cortical plasticity in chronic smoking schizophrenia patients (Strube et al., 2015). In addition, tDCS interventions have proven capable of reducing various substance-related behaviors and craving (e.g. Boggio et al., 2008; Boggio et al., 2010; Falcone et al., 2016; Fregni et al., 2008; Klauss et al., 2014; but see Smith et al., 2015 for a negative finding). In light of the high prevalence of substance use in the schizophrenia population, and its potential as a significant moderator and outcome variable (albeit ancillary to our main hypotheses), we will track substance use throughout intervention.

3.0 Study Endpoints/Events/Outcomes

3.1 Primary Endpoint/Event/Outcome:

SA1. Compare the effect of right active-tDCS, left active-tDCS and sham (hemisphere) in HC, the effect of left active-tDCS and sham in SZ, length of treatment and measured dosage on brain circuitry. In both HC and SZ, greater ipsilateral thalamocortical (prefrontal) FC increases relative to sham are driven by **H1.1** active tDCS in the ipsilateral hemisphere; **H1.2** a longer length of treatment; and **H1.3** higher modeled dosage.

SA2. Establish the effects of hemisphere, length of treatment and modeled dosage on generalization and durability. In both HC and SZ, greater generalization and durability are driven **H2.1** more by right tDCS compared to left tDCS or sham; **H2.2** by a longer length of treatment; and **H2.3** by higher modeled dosage.

SA3. Examine how changes in thalamocortical FC in both hemispheres affect generalization and durability. In both HC and SZ, greater thalamocortical FC drives **H3.1** greater generalization; and **H3.2** greater durability.

SA4. Examine relationships between genetic variants, epigenetic changes and treatment outcome (e.g. generalization, durability, functional connectivity).

4.0 Study Intervention(s)/Investigational Agent(s)

4.1 Description:

This study will include 2 cohorts of participants (healthy controls and patients with schizophrenia) in order to evaluate how anodal tDCS with concurrent WM focused training affect thalamocortical connectivity, how this may differ from right vs. left (hemisphere) vs. sham stimulation, how the number of sessions (length of treatment) and modeled dose impacts proximal transfer and generalization, how they are affected by other psychologically and biologically relevant variables, and the durability of these cognitive changes after training.

PROTOCOL TITLE: Increased thalamocortical connectivity in tDCS-potentiated generalization of cognitive training

VERSION DATE: January 26, 2023

For the proposed project, participants in cohorts 1 and 2 will undergo a similar protocol, consisting of WM training concurrent with tDCS. This training will consist of a target of 30 sessions of 45 minutes each in 11-12 weeks (target average density of 3 sessions/week), with a minimum of 24 sessions (and a minimum average density of 2/week). Due to limited reach to the schizophrenia population during the global pandemic, cohort 2 is expected to be a smaller sample size than originally anticipated. We will only be studying left hemisphere stimulation in cohort 2 subjects.

The tDCS will be performed with Neuroelectrics Starstim8 (Neuroelectrics Barcelona, Spain). This device has been approved for use in research without an investigational device exemption due to meeting criteria for non-significant risk. In addition, the device has built in safety mechanisms which allow for the immediate cessation of stimulation should the subject become uncomfortable or impedance levels too high.

The Starstim software supports the measurement of electrode impedance (Neuroelectrics, 2016). Before each training session, the impedance of the electrodes will be checked and verified to be ≤ 10 KOhm. During a training session, the impedance is measured every second and if found to be > 20 KOhm stimulation will be terminated for safety. The current and impedance will be recorded for every session (Ruffini, 2016) (implemented in Dec 2016, NIC v2.1).

We will take advantage of the ability of the Neuroelectrics StarStim8 (Neuroelectrics Barcelona, Spain) unit to programmatically control stimulation at multiple electrodes. During the intervention, subjects will wear a headband with electrodes at AF4 and AF3 (right and left DLPFC). Three different stimulation montages will be programmed: right, left and sham. Stimulation will consist of three periods: RampUp (30 sec), Constant (20 min), RampDown (30 sec). During the Ramp periods, 2 mA current will be delivered to both AF3 and AF4 with an ascending (RampUp) and descending ramp (RampDown) over 30 sec via two saline soaked electrode sponges ($\sim 25\text{cm}^2$; current density = 0.08 mA/cm 2). In this way, all subjects experience the same sensation on both sides to blind them to condition. During the Constant period, current will be set based on the Condition: Right - 2mA AF4 anode-AF3 cathode; Left - 2mA applied to AF3 anode-AF4 cathode; Sham - current turned off. We will test and adjust this new blinding approach on healthy subjects prior to beginning the formal study. To assess subject perceptions of the intervention, we will ask what treatment they believe they received each session.

A second stimulation device will also be available for use in the study. The TaskFlow Transcranial Electrical Stimulation device (TaskFlow-TES) is a custom brain stimulation device developed in-house at the University of Minnesota. The TaskFlow-TES has been designed to provide the same functionality as the commercial device we are currently approved to use (Neuroelectrics StarStim8). Like the StarStim, the TaskFlow-TES is battery powered, communicates with the control computer via Bluetooth and monitors impedance and delivered current.

- 4.2 IND/IDE: N/A
- 4.3 Biosafety: N/A
- 4.4 Stem Cells: N/A

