Assessment activities may be audio/video-recorded. These data will be reviewed by the study team in order to achieve reliability and consistency between different interviewers and to arrive at consensus ratings for assessment scores. Assessment audio/video data will be stored on a secured UMN Box server and will only be accessible by the study team. Participants will have the choice to opt out of assessment audio/video recording in the consent form.

In addition, all participants will provide a urine or saliva sample in order to complete a drug screen. Results will be recorded.

HC participants will be randomly assigned to one of the 3 groups: (i) Active 2mA right (AF4 anode-AFP3 cathode) or (ii) Active 2 mA left (AF3 anode-AFP4 cathode), or (iii) Sham 0 mA tDCS during concurrent WM focused training for a total of 12 weeks. SZ participants will be randomly assigned to one of the 2 groups: (i) Active 2 mA left (AF3 anode-AFP4 cathode), or (ii) Sham 0 mA tDCS during concurrent WM focused training for a total of 12 weeks. Neither participants nor experimenters will know group assignment. TDCS software programming will allow staff selection of the three hemisphere conditions (right, left, sham) corresponding to eight random letters (six to be distributed evenly among three conditions for HCs, two to be distributed evenly among two conditions for SZs) encoded to preserve the blind. Randomization will be facilitated and the blinding code will be maintained by the study statistician.

Neuroimaging Assessments/MRI (Baseline, Week 6, Week 12):

Participants who are able to do in-person study visits will complete MRI sessions using the 32 channel head coil on a 3T Siemens Prisma scanner (Siemens Erlangen, Germany) located in the Center for Magnetic Resonance Research (CMRR) at the University of Minnesota at baseline, midway through the intervention and post-intervention, at 12 weeks. MRIs will not be completed if there is any concern for participant safety. This includes safety concerns during the COVID-19 pandemic.

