15.0 Statistical Considerations

15.1 Data Analysis Plan:

Analyses to test SA1, whether ipsilateral thalamocortical (prefrontal) FC changes are affected by hemisphere, length of treatment or modeled dosage will be conducted separately for Studies 1 and 2. We will use FSL Randomise (“Randomise/UserGuide - FslWiki,” n.d.) using non-parametric thresholding (5000 permutations, p-value 0.001) to avoid inflated false positive rates (Eklund, Nichols, & Knutsson, 2016), and threshold for significance using threshold free cluster enhancement (TFCE). Randomise design matrix files and contrast files (“GLM - FslWiki,” n.d.) will model specific contrasts to compare the effect of right v. left active-tDCS or sham on thalamo-prefrontal FC. Main effects of hemisphere (right active-tDCS vs left active-tDCS and sham-tDCS H1.1), length of treatment (H1.2), and modeled dosage (H1.3) will be examined for each fMRI dataset (rest, N-Back, and DPX). Group x Time (pre-intervention, mid-intervention, post-intervention) interactions will also be examined for each fMRI dataset. In addition to motion correction and motion-related artifact removal, 24-parameter motion estimates will be included as regressors of noninterest (Power, Schlaggar, & Petersen, 2015). Rest. Rest will provide the most straightforward use of the regressor, which is to detect whether changes in thalamocortical connectivity exists. Since this test is in the absence of particular task demands any changes noted suggest trait-related functional connectivity changes. N-Back. Task-dependent connectivity associated with N-back task performance will be identified by modeling the block task design together with the thalamic regressor (similar to psychophysiological interaction (PPI) analysis (Friston et al., 1997)). Blocked fMRI analysis will allow us the best power to detect hemodynamic changes within brain networks related to working memory. The primary analysis for the N-Back tasks will consider the 2-back conditions alone. Subsequent analyses will examine the 2 > 0-back contrast to strengthen interpretation of any observed changes in task-dependent thalamocortical connectivity. DPX. Task-dependent connectivity associated with the DPX task demands will be identified by analyzing cue and probe events together with the thalamic regressor. Preliminary analysis for the DPX task will examine B-cue related connectivity alone, as this draws the most on proactive, WM-dependent, control. Subsequent analyses will strengthen interpretation by examining both B-cue > A-cue related connectivity, as well as connectivity changes associated with response-related, or reactive, control (during the AY condition). These analyses can all be completed before the blind is broken, with direction of any effects to be resolved after breaking the blind.

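### In Cohort 1 the contrast that section 15.1 assigns to H1.1 (right v left and sham) does not test H1.1 as section 3.1 states it, and H1.1 has no valid left-hemisphere test

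*Combined protocol and SAP*

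**What the plan says.** **Hypothesis (section 3.1, SA1).** In both cohorts, "greater ipsilateral thalamocortical (prefrontal) FC increases relative to sham are driven by" active tDCS in the ipsilateral hemisphere (H1.1). The comparator is sham, and the claim applies to whichever side is stimulated.

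**Montage (section 4.1; the same pairing in 5.1 and the tDCS protocol in 5.2).** During stimulation "subjects will wear a headband with electrodes at AF4 and AF3 (right and left DLPFC"), and the conditions are "Right - 2mA AF4 anode-AF3 cathode; Left - 2mA applied to AF3 anode-AF4 cathode; Sham - current turned off". The randomization paragraph of 5.2 instead writes "i) Active 2mA right (AF4 anode-AFP3 cathode) or (ii) Active 2 mA left (AF3 anode-AFP4 cathode"). These passages must be reconciled. In either wording the cathode lies on the side opposite the anode, so the point below does not change.

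**Analysis (section 15.1).** The contrast files will "model specific contrasts to compare the effect of right v. left active-tDCS or sham on thalamo-prefrontal FC". The test labelled for the hypothesis is "Main effects of hemisphere (right active-tDCS vs left active-tDCS and sham-tDCS H1.1"). No weights are given, and neither right v sham nor left v sham is named as the H1.1 contrast. The section adds that "Group x Time (pre-intervention, mid-intervention, post-intervention) interactions will also be examined for each fMRI dataset", and it leaves the direction of effects to be settled after unblinding.

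**Cohort 2 (sections 4.1 and 5.1)** has only left and sham arms.

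**The concern.** The hypothesis and its labelled test have different shapes. H1.1 predicts a gain over sham in the right hemisphere for the right arm and in the left hemisphere for the left arm. A contrast of right against left and sham has the shape of H2.1 (right better than left or sham), and it treats the left arm as a control. In the left hemisphere, the arm predicted to improve is therefore counted against the hypothesis.

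The second issue is the comparator. Both active arms pass 2 mA between the same two prefrontal sites. For right-hemisphere FC, the left arm is a group with a cathode over the region of interest; it is not an untreated group. Whatever the cathode does enters the contrast alongside what the anode does.

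H1.1 belongs to the first aim listed under the primary endpoint heading. An analyst who follows the label would report a result that does not answer the stated question in one hemisphere and may mix two effects in the other.

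**Working it through.** **The plan's own imaging figure.** Section 15.2 says the study can detect group x time voxel differences of η² = 0.07 at α = .001. With 75 completers, three groups, two time points and an assumed within-person correlation of 0.5, f² = 0.07/0.93 = 0.0753 and λ = f² × 75 × 2/(1 − 0.5) = 22.6 on 2 and 72 df. Power is 0.82, and the smallest η² detectable with power .80 is 0.067, which matches the printed 0.07 after rounding. That figure concerns the omnibus interaction. It says nothing about which contrast tests H1.1.

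**Inputs.**
- Arms and polarity: section 4.1.
- Comparator for H1.1: section 3.1.
- Contrast: section 15.1, read as right − (left + sham)/2. The equal weights are an assumption.
- Completers: 25 per cell, section 15.2.
- a = anode-side effect and c = cathode-side effect on FC change, each relative to sham and taken as equal in the two hemispheres. The documents give no value for either.

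**Expected values.**
- Right hemisphere: right arm = a, left arm = c, sham = 0. Contrast = a − c/2.
- Left hemisphere: right arm = c, left arm = a, sham = 0. Contrast = c − a/2.
- H1.1 itself, right arm v sham on the right and left arm v sham on the left: a in each.

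| Assumed (a, c) | H1.1 target, each side | Contrast, right | Contrast, left |
|---|---|---|---|
| (1, 0) | +1 | +1.0 | −0.5 |
| (0, −1) | 0 | +0.5 | −1.0 |
| (1, −0.5) | +1 | +1.25 | −1.0 |

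The first row needs no cathodal effect: the right side is correct, and the left side has the wrong sign and half the size. Right v left alone gives a − c on the right, so it is also positive when a = 0 and c < 0.

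Reversing the contrast for the left hemisphere does not help. (Left + sham)/2 − right = a/2 − c, which gives the right arm's cathodal effect full weight and the left arm's anodal effect half weight.

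**Precision (change-score SD units, 25 per arm).**
- Pooled contrast: SE = √[(1 + 1/4 + 1/4)/25] = √0.06 = 0.245.
- One arm v sham: SE = √(2/25) = √0.08 = 0.283.

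**Probabilities (noncentral t, 72 df, two-sided tests, one prespecified comparison).** These do not model the permutation and cluster-enhancement procedure, so they show scale only.
- H1.1 true, a = 0.8, c = 0, left hemisphere: expected contrast −0.40. At α = .05 the chance of a significant positive result is 0.0002 and of a significant negative result 0.36.
- No anodal effect, right hemisphere, with assumed c = −0.5, −0.8 and −1.0: the chance of a significant positive result is 0.17, 0.36 and 0.52 at α = .05 (nominal upper tail 0.025), and 0.011, 0.043 and 0.093 at α = .001 (nominal 0.0005).
- a = 0.8, c = 0, right hemisphere: power of the pooled contrast v right v sham is 0.90 v 0.80 at α = .05, and 0.44 v 0.29 at α = .001.

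**The case against.** **The pooling is a reading of one parenthesis.** No weights are printed, the preceding sentence speaks of contrasts in the plural, and the same text serves Cohort 2, which has no right arm. Two separate comparisons may be meant. This stands as a caveat: right v sham would then be sound. Right v left would still mix a and c, and left v sham would still be missing.

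**No document says the cathode lowers thalamocortical FC.** Section 2.3 reports only comparably small results for cathodal stimulation, and those concern cognition. This also stands. With c = 0 the right-hemisphere contrast is unbiased, and with c > 0 it is conservative. A reader might infer that a false positive is to be expected, or that the right-hemisphere result is wrong in any case. The documents support neither. The left-hemisphere mismatch does not depend on c.

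**The two hemispheres together carry the information.** With x the right-hemisphere and y the left-hemisphere contrast, mirror symmetry gives a = (4/3)(x + y/2) and c = (4/3)(y + x/2). It would therefore be too strong to say that pooling destroys the separation of anodal and cathodal effects. But this recovery needs equal effects in both hemispheres, and section 15.1 plans no such step.

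**Other analyses would show a problem.** The group x time interaction and the reading of direction after unblinding would expose a negative left-hemisphere sign. Neither separates anodal gain from cathodal loss, and neither states in advance what would count as support for H1.1.

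**Conclusion.** The point holds for Cohort 1. The contrast labelled for H1.1 does not match the hypothesis in section 3.1, and section 15.1 names no contrast that tests H1.1 in the left hemisphere. On the plain reading with equal weights, a true anodal gain a with no cathodal effect appears as +a on the right and −a/2 on the left.

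The weakness of the left arm as a comparator for right-hemisphere FC is conditional. It matters only if the cathode has an effect, whose direction and size the documents do not give. The 0.17 to 0.52 chance of false support at α = .05 rests on an assumed decrease of 0.5 to 1.0 SD.

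A reader might go further and conclude that the plan certainly pools the arms, that the montage is at fault, or that H1.1 should stand only if both hemispheres are positive. The text does not fix the weights. The montage is openly defined, and this point gives no reason to change it. Section 3.1 can be tested one hemisphere at a time. Cohort 2 already compares left with sham and is not affected.

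**What to change.** In section 15.1, state that H1.1 in Cohort 1 is tested by two prespecified contrasts against sham alone:
- right arm v sham on right thalamo-prefrontal FC;
- left arm v sham on left thalamo-prefrontal FC.

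Interpret each for its own hemisphere. Report the two cathode-side contrasts v sham, and right v left, as secondary or descriptive. Print the contrast weights, and make the change before unblinding.

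The cost is new Randomise contrast files, a short text change and a modest loss of precision on the right: SE 0.283 instead of 0.245 SD. At an assumed 0.8 SD effect with no cathodal effect, power falls from about 0.90 to 0.80 at α = .05 and from 0.44 to 0.29 at α = .001. No new data or participants are needed.
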